## **SUMMARY OF PROJECT 2 SUPPLEMENT (06/2015)**

The goal of project 2 is to transform the management of pancreatic cancer (PanCa), a devastating disease that is most often diagnosed in later stages, when curative therapies are unlikely. This strategy starts with a target of advanced or locally advanced pancreatic cancer (LAPC) with a phase II trial of photodynamic therapy (PDT) to evaluate local destruction of the tumor. This is later followed by a combination therapy of PDT and MM398, as a secondary goal of treating metastatic disease. This initial Phase II trial is the stepping stone towards the more needed combination therapy trial, which has the potential of seriously impacting long term survival of these patients. ***As such, we are proposing to expedite the Phase 2 by creation of a multi-center trial, combining patients at the University College London Hospital with a new two sites in the Mayo Clinic Health System (Rochester, MN). This approach should increase the recruitment rate, and lead to a faster completion, allowing earlier transition to the combination therapy trial, and also brings part of the study to the United States for evaluation here.*** This trial will utilize a minimally invasive approach of endoscopic ultrasound (EUS)-guided PDT, with the goal for outpatient therapy with improved safety and healthcare costs. Together, the UCLH and Mayo clinic will establish, in a multicenter phase II study, the efficacy of EUS-PDT using verteporfin (benzoporphyrin, BPD) to ablate solid tumors of the pancreas. Clinical contrast CT-based treatment planning will be used to deliver patient-specific PDT in the trial as well, adding additional dosimetry innovation to the study. The study will recruit both localize advanced pancreatic cancer and metastatic disease, that will also establish the safety of giving chemotherapy almost immediately after PDT. The immediate impact of this project will be to improve the care of patients with PanCa, and more broadly the findings will establish a clinical framework to translate new nanomedicine and combination-based targeted therapeutic discoveries for cancer.

**Potential public health benefits:** The clinical studies described above provide new minimally invasive treatment option aimed at improving the length and quality of life in patients with PanCa. Rapid control of local disease can help alleviate obstructive symptoms and increase tolerance to systemic therapy. The multi-center approach to the trial will bring the treatment to the United States for evaluation in our healthcare system, as well as expedite the results of the trial, to allow the eventual combination trial to be completed in a more efficient manner.

## SPECIFIC AIMS

The overall aim of this supplement is to contribute to improved treatment of pancreatic tumors, using the minimally invasive technique of endoscopic ultrasound (EUS)-guided PDT and CT-based dosimetry as a predictive tool for treatment planning, which was shown to be a key element in this program project. The five-year survival of PanCa is less than 6% and this has remained unchanged over the last four decades. This work follows on from the PI, Dr.[name]'s recently completed phase I clinical study of verteporfin PDT in patients with PanCa. In this dose escalation study, it was demonstrated that PDT can be delivered safely to patients with locally advanced cancers, with an increase in the diameter of necrosis with increasing light dose. The phase II proposed follow up will confirm that beyond safety, that PDT can yield good local control of pancreas disease. These studies will then inform the design of future studies of PDT + advanced chemotherapy combinations, as proposed in the last aim of the Project 2. The primary goal of this supplemental study is to assist the Phase 2 recruitment and trial by doubling the number of subjects that can be recruited, and power the study to assess

### **Hypothesis 1: EUS-guided PDT will provide effective ablation of solid lesions of the pancreas (multi-center phase II clinical trial at UCL + Mayo).**

Clinical use of PDT for PanCa has been pioneered by the Project 2 group, and a positive correlation was established between delivered energy and the extent of tumor necrosis around interstitial fibers, with no serious adverse events. We aim to improve the approach by moving to a minimally invasive approach of EUS, in conjunction with dosimetry to monitor treatment (jointly with *Project 4*).

**Aim 1.** To participate in the conduct a phase II study of EUS-guided PDT in PanCa. PDT will be done initially at a single site with a fixed light dose for the first group of patients, then at multiple sites to match the zone of tumor necrosis to tumor volume.

This work will lead into the next logical step in the trial, which was the major goal of Project 2, namely a combination therapy trial using PDT, standard chemotherapy and in patients with advanced or locally advanced and metastatic disease. The advanced cancer patients will be defined as patients with at least a 50% increase in tumor volume or new metastasis regardless of whether the patients had chemotherapy. All participants will be within ECOG performance status of 0-2. This work provides a direct bench-to-bedside translation, as we will use the most effective combination sequence form project 3 as they study in pre-clinical work. While this is not the goal of this current supplement, it is a future direction, which will be expedited by the completion of this proposed Phase II trial.

After intravenous administration of verteporfin, fluorescence readings will be taken from the patient's buccal mucosa to register the fluorescence peak. This is performed using a mobile fluorimeter that uses an ipad as the processor. The device delivers a very small amount of light to the buccal mucosal and can measure nanogram levels of drugs. A gradient spectrophotometer is coupled to a CCD to record the fluorescence. Background fluorescence will be performed earlier in the day from the same area of buccal mucosa. The measurements will be taken every 10 minutes until the procedure (total 6-9 measurements).

We plan to take FNA biopsies of the lymphocytes to assess immune response due to treatment.

## Research Strategy

### a) SIGNIFICANCE

The goal of this project is to transform the management of pancreatic cancer (PanCa) in the advanced or locally advanced, and metastatic phases, using PDT in combination with systemic therapy. Specifically, we will build on our previous phase I findings of PDT-induced tumor necrosis in PanCa patients that has been shown to be safe without significant toxicities, and move to the minimally invasive approach of EUS-guided PDT, with the potential for outpatient therapy with improved safety and healthcare costs. Prior studies in a mouse xenograft model of pancreatic cancer at the Mayo Clinic also demonstrated the potential efficacy of next generation photosensitizers in photodynamic therapy. In particular, given that most pancreatic cancers consist of fibroblasts that encase tumor cells, it appears logically to have a locally delivered therapy which could potentiate additional chemotherapeutic agents. We will allow early delivery of chemotherapy after this therapy and observe if this can enhance the effectiveness of chemotherapy. Single therapies alone are ineffective in PanCa, it is hypothesized that this combination strategy will enhance survival of patients who have advanced or locally advanced and/or metastatic disease. We will also use EUS-PDT in patients with premalignant cystic neoplasms of the pancreas, which carry a significant risk of cancer development.

#### a.1: Pancreatic Cancer

Worldwide, PanCa is one of the top 10 leading causes of cancer deaths, and ranks fourth as a cause of cancer death in the UK and USA (1). Overall, the long term prognosis of the disease is poor with a one-year survival rate of no more than 10%. For cancers staged more advanced than Stage 1B, 5 year survival is less than 7%. For non-metastatic disease, median survival is 6–10 months although for those with metastatic disease at presentation, survival is only 3–6 months (2, 3). While there have been small gains in therapeutic options for patients in recent years, there has been no significant improvement in overall outcome for more than two decades. Novel treatment strategies for advanced tumors and improved detection and ablation of premalignant lesions are necessary to improve outcome.

According to the SEER (Surveillance, Epidemiology, and End Results Program) database, it is projected that there will be 48,760 new cases of pancreatic cancers in the United States (incidence of 10.4/100,000) with a five year projected survival rate of only 7.2%. The lifetime risk of developing pancreatic cancer is 1.5% in both men and women. There is also estimated to be 40,560 deaths due to pancreatic cancers in 2015. There has not been a major advancement in survival with unresectable pancreatic cancer that is the primary rationale for the development of new innovative therapies such as photodynamic therapy.

#### a.2: Current treatment of pancreatic cancer

In series from specialized centers, over 10% of patients may be resectable at presentation, but in larger population-based studies the number undergoing resection with curative intent may be as low as 3% (4, 5). Even after resection, median survival is only 10–20 months and no more than 5–20% of resected patients survive more than five years (6). Options available for the treatment of inoperable patients are largely limited to chemotherapy, radiotherapy, or some combination of the two. In both the US and Europe, gemcitabine is the most commonly used agent. The UK GemCap study - a phase III multicenter randomized clinical trial comparing gemcitabine alone or in combination with capecitabine for the treatment of 533 patients with advanced PanCa – reported a median survival in the combination capecitabine + gemcitabine group of 7.1 months compared with 6.2 months in those who received gemcitabine alone, with 1-year overall survival rates of 24.3% vs 22% (HR = 0.86; P=0.077) (7). The French randomized study of FOLFIRINOX (fluorouracil, leucovorin, irinotecan and oxaliplatin) versus gemcitabine chemotherapy, showed a significantly improved survival in the FOLFIRINOX group (median 11.1 vs 6.8 months; hazard ratio [HR] = 0.57; P<0.001) (8). A phase III study of weekly intravenous albumin-bound paclitaxel (nab-paclitaxel) plus gemcitabine resulted in a significantly higher overall survival compared with gemcitabine monotherapy (8.5 vs 6.7 months; HR = 0.72; P<0.001), with survival rates of 35% versus 22% at 1 year (9). Further studies into combination regimens are needed. Trials of biological agents such as VEGF inhibitors in advanced disease have been largely unsatisfactory (10). The Canadian phase III trial of gemcitabine with erlotinib (a small molecule EGFR inhibitor) compared to gemcitabine alone, showed a significantly improved overall

survival in the combination arm, albeit with a median survival of only 6.2 vs. 5.9 months (11). Overall, the long-term prognosis of the disease is poor. Given these dismal results, surgical debulking or interstitial ablation has been investigated as a potential additional therapy in PanCa. In a recent systematic review comparing R2 resections to palliative bypass alone in the management of advanced pancreatic ductal adenocarcinoma (PDAC), a small non-significant survival advantage was observed in the R2 resection group; 8.2 months compared to 6.7 months in the palliative bypass group. However patients undergoing R2 resections had a significantly higher morbidity (RR: 1.75, 95% CI 1.35–2.26;  $P<0.0001$ ), mortality (RR: 2.98, 95% CI 1.31–6.75;  $P=0.009$ ) and a longer hospital stay (mean difference, 5 days; 95% CI 1–9 days;  $P=0.02$ ), so that R2 resections cannot be recommended as part of standard management (12). In considering better alternatives, minimally invasive ablative therapies delivered percutaneously or endoscopically have become part of standard therapy in many other solid organ tumors, particularly in patients with inoperable disease or in patients unfit for surgical resection.(13) We therefore believe that for PanCa, a minimally invasive treatment capable of local destruction of tumor tissue with low morbidity may have an important place in the treatment of this disease.

### **a.3. Future treatment: Advantages of Endoscopic versus Percutaneous delivery of PDT for PanCa**

PDT is a targeted anti-cancer treatment modality that has been extensively investigated in preclinical PanCa models by our group for mTHPC (14) and verteporfin (15) mediated PDT. These studies showed safety and efficacy in both normal tissues and transplanted tumors. We have also performed initial clinical studies of PDT for PanCa using mTHPC and CT-guided, percutaneous needle placement. Our group has shown feasibility, safety to surrounding normal tissues and successful induction of tumor necrosis; indicating that PDT was useful for local debulking of PanCa (16). These results motivated a Phase I clinical study using verteporfin-mediated PDT - chosen over mTHPC due to a reduced drug-light interval and photosensitivity times. We will develop a similar protocol for EUS-guided PDT of cystic tumors of the pancreas. Based on our own published experience with endoscopic PDT and EUS-FNA (17, 18), we expect EUS-PDT to be associated with a very low side effect profile and fewer complications than interstitial PDT or EUS-guided alcohol injection or radiofrequency ablation and will be an ideal therapy for those who are unfit for surgery or who have premalignant lesions who would otherwise require long-term surveillance. EUS-PDT represents a highly innovative approach towards day case anticancer therapy.

**Fig. 1. a)** Light delivery after CT-guided insertion of multiple 19G needles into the pancreas under local anaesthetic and i.v. sedation. **b)** Endoscopic delivery of PDT under conscious sedation.

### **a.5: Experimental Treatments for Locally Advanced Pancreatic Cancer at the Mayo Clinic**

The Mayo Clinic currently is the site of a Pancreatic Cancer SPORE headed by [name]. The institution has been very active in the development of potential therapies for pancreatic cancer. Several recent studies have involved potential new therapeutic pathways. This includes a recently published study investigating the use of inhibitors of Nampt to decrease pancreatic cancer cell growth in vitro and in vivo animal models. This is a novel approach that targets the NAD salvage synthesis pathway and inhibition of Nampt was found to decrease lactate production, mitochondrial function, and ATP. In addition, CD38 which is an NADase was found to modulate this effect. Lowering the level of CD38 decreased the response of Nampt to inhibition which was a novel observation. This pathway might well enhance the effects of PDT on pancreatic cancer (57). Mayo Clinic researchers also recently published on the advantages of the combined effects of TRAIL and GSK-3 inhibitors on increasing apoptosis in pancreatic cancer cell lines resistant to apoptosis. These investigators found that overexpression of GSK-3B led to resistance to pro-apoptotic signaling from TNFa and TRAIL through anti-apoptotic genes such as Bcl-xL. This was reversed by inhibition of GSK-3B. These observations lend further rationale to the addition of GSK-3 inhibitors to TRAIL for therapy of pancreatic cancer (58). These are only a sample of the studies that have been developed through our Pancreatic Cancer Spore.

Efforts have also been made to characterize young onset pancreatic cancer in a study being conducted at the Mayo Clinic that is collecting genetic information on all patients with pancreatic cancer diagnosed earlier than age fifty. It is hoped that specific genetic patterns can be detected to determine if there are underlying mechanisms for these younger patients. This study is being conducted by [name]. Novel therapies are also being investigated such as the use of immunotherapy in conjunction with stereotactic body radiation to treat locally advanced pancreatic cancer. Mayo Clinic is part of the Alliance for Clinical Trials in Oncology which consists of approximately 10,000 oncologists sponsored by the NCI. As part of these multi-center trials, Mayo is involved in studies using Abraxane and gemcitabine in local pancreatic cancer, Nivolumab with Abraxane and carboplatin in advanced pancreatic cancer, and rucaparib in patients with pancreatic cancer and a known BRCA mutation among several others. We also participate with the RTOG to investigate the effects of high or standard intensity radiation therapy in combination with chemotherapy. This wide variety of studies increases the likelihood of referrals to our institution for this novel protocol. Based on our past recruitment, the Mayo Clinic Rochester treats about 80 patients a year with locally advanced pancreatic cancer every year for the last 5 years. We believe that it would be reasonable to anticipate that we could recruit at least 5 patients into this study each year.

### **b.INNOVATION**

Key innovations in this proposal are:

1. Development of the minimally invasive technique of EUS-guided PDT to provide effective, minimally invasive ablation of solid tumors of the pancreas (Phase II clinical trial). For patients choosing additional conventional chemotherapy, this will also provide the opportunity to assess the safety of giving chemotherapy in much closer time relationship to PDT than previously.
2. Use of contrast-CT as a clinically implementable technique for optimizing the light dose to predict the extent of PDT necrosis and so match this to the extent of disease without causing any unacceptable damage to adjacent normal structures.
3. Assessment of pancreatic tissue immediately preceding photoradiation to assess for verteporphyrin concentrations and potential biomarkers for response.

#### **b.1 EUS-guided PDT will enable effective ablation of solid tumors of the pancreas.**

Based on our collaborators at the University College London's previous animal experimental work, and our pre-clinical and clinical trials of pancreatic PDT, a phase I study of verteporfin PDT in locally advanced unresectable PanCa (VERTPAC-01) was undertaken. In the initial dose escalation part of the study, patients were treated with verteporfin PDT to assess its general safety profile, to determine the optimum treatment parameters needed to achieve effective and safe necrosis of tumor, and to confirm safety of administration of subsequent conventional palliative chemotherapy. Inclusion criteria included a histopathological/cytological diagnosis of PanCa, unresectable, non-metastatic disease confirmed at multidisciplinary review and adequate biliary drainage (serum bilirubin < 2.5 x upper limit of normal). All patients received a dose of verteporfin 0.4 mg/kg bodyweight intravenously, followed by light activation 60 minutes later under subdued lighting conditions. Treatment was via a single 10 mm tip diffuser fiber which was placed under CT guidance by an experienced radiologist (Figure 1). With increasing light doses, there was an increase in the extent of tumor necrosis around the fiber with no serious adverse events or reports of photosensitivity. This study aims to replicate these findings using the minimally invasive approach of EUS. Initially, only a single position of the laser fiber will be used, but in later patients multiple fiber positions will be used to show that it is possible to treat the full volume of appropriate cancers with endoscopic placement of the treatment fiber in more than one site. This is essential to show that endoscopic fiber placement can cover a comparable volume of tumor to the multi-fiber, percutaneous approach used in the previous studies.

**Fig. 2. Patient undergoing verteporfin PDT.** The image on the left shows a baseline contrast-enhanced CT with a low attenuation mass in the head of the pancreas. The centre image shows percutaneous needle placement into the tumour. The image on the right shows the day 5 post PDT contrast-enhanced CT with a  $2.67 \text{ cm}^3$  zone of necrosis in the region of the pancreatic head.

### b.2: Use of contrast-CT to predict PDT response.

As reported in Project 4 and Core C, retrospective analysis of our Vertpac data showed that the CT venous phase contrast enhancement (when compared with CT without contrast), a measure of the blood concentration around the target zone, was strongly correlated with the volume of necrosis per unit of light energy deposited. This indicates that CT contrast should be a useful dose planning guide in future trials with photodynamic therapy.

## c. APPROACH

### c.1 (Aim 1) Phase II study of EUS-guided verteporfin PDT in solid pancreatic tumors (VERTPAC-01)

[figure not shown]
#### c.1.a Objectives

**Primary:** To show that EUS-guided PDT to the pancreas is effective at direct ablation of advanced or locally advanced and small volume metastatic pancreatic tumors **in a multicenter setting.**

**Secondary:** To evaluate the predictability of tumor necrosis as a function of delivered energy, based on pre-PDT contrast CT scans.

**Tertiary:** Evaluate the safety of chemotherapy given two days after PDT

**Quaternary:** Demonstrate that cancer biomarkers in pre- vs. post-PDT are surrogate markers of response.

**Fig. 4.** Linear echoendoscope with optical diffuser fibre (arrow) extending from a 19G FNA needle.

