#### c.1.b Design of VERTPAC-02 study

This will be a phase II study of 15 (UCL) + 15 (Mayo) patients with histologically proven advanced or locally advanced PanCa or other solid tumors unsuitable for surgical resection. In the first 5+5 patients, EUS guided verteporfin PDT will be used with light delivered at just one site. In the following 10+10 patients, light will be delivered with the fiber at multiple positions, as required to ensure treatment of all appropriate areas of the cancer, as was done in the previous studies with percutaneous fiber insertion. Each patient will be given verteporfin 0.4 mg/kg bodyweight intravenously, followed by light activation 60 minutes after photosensitization (acceptable treatment window 60- 90 minutes). Light delivery will take place via a 5-20 mm length diffuser fiber placed under EUS guidance using red laser light at 690nm. The light dose delivered down the fiber will be fixed at 40 -80 J/cm, which was found to be optimum in our previous VERTPAC-01 study. All patients will be prescribed ciprofloxacin as a prophylactic to reduce the potential risk of infection associated with the fine needle puncture of the tumor. If a patient is allergic to ciprofloxacin, another acceptable broad spectrum antibiotic will be prescribed at the investigators discretion.

Patients will be evaluated by contrast enhanced CT at 2 days after PDT (treatment day 3), and they will be able to commence conventional palliative chemotherapy after that if they so wish within a week of PDT. Patients will also have additional blood draws taken for biomarker analysis before, during, and after their treatment. In previous studies, it was a protocol requirement that chemotherapy

not be given within a month of PDT. However, PDT is a local, one off treatment and chemotherapy is systemic and ongoing. It is an important innovation to give chemotherapy much earlier after PDT as our previous study on PDT for biliary tract cancer showed that delay in giving chemotherapy after PDT put patients at a disadvantage. Treatment response and time to disease progression will be assessed by CT scans at three-monthly intervals, as part of usual practice. Thereafter, patients will continue to be followed up for survival data. Second line chemotherapy and/or re-treatment with verteporfin PDT for progressive disease will be at the discretion of the investigators.

**c.1.c Patient eligibility:** See Table 1.

Inclusion Criteria	Exclusion Criteria

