### c.1.d Pre and post procedure assessments:

See Table 2.

TABLE 2. Pre- and Post-Procedure Assessments for the VERTPAC-02 Study

Timepoint	Assessment
Pre-procedure	
 
Informed consent
 
Symptom and adverse event monitoring
 
Physical examination (including weight and ECOG performance status)
 
FBC, INR and biochemical profile including tumor markers (CEA/CA19-9), amylase, glucose
 
Pancreatic protocol CT chest, abdomen & pelvis (day -28 to 0)
 
Copy of report of prior histological or cytological proof of PanCa
 
QOL forms (EORTC QLQ30)
 

Post procedure	
 
Following treatment, patients will be monitored closely on the ward. The following protocol will be used to assess patients post treatment
 

Day 2 and 3 after the treatment on Day 1	
 
Symptom and adverse event monitoring, physical examination (including ECOG performance status)
 
FBC and biochemical profile including amylase, glucose
 
Pancreatic protocol CT on day 3, prior to planned discharge
 

Day 14	
 
Symptom and adverse event monitoring, physical examination (including ECOG status)
 
FBC and biochemical profile including amylase, glucose
 
QOL forms (EORTC QLQ30)
 

Months 3, 6 and 12:	
 
Symptom and adverse event monitoring; physical examination (including weight and ECOG status)
 
FBC and biochemical profile including CEA/CA19-9
 
Pancreatic protocol CT
 

Clinical and laboratory assessments will be repeated prior to discharge (anticipated at day 3). All patients will be followed up on day 14 then at three, six and 12 months. At each visit, clinical symptoms will be reviewed, and quality of life and laboratory assessments repeated. In patients in good general condition with evidence of residual tumor or local tumor progression on repeat CT, up to two further PDT treatments may be offered at a minimum of four week intervals. If patients are unable to return for follow up they will be contacted by phone to complete the QOL assessment, as well as asked if they have had adverse events, hospitalization related to disease or progression of disease.

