##### **SECONDARY Response evaluation**

- Progression-free survival will be determined at 6 months follow-up and beyond.
- CEA and/or CA19.9 4-weekly if elevated prior to therapy
- ECOG performance status and Brief Pain Inventory pain scores, prior to therapy and at follow-ups
- Comparison will be made between the documented extent of necrosis and both the measured photosensitizer concentration, as assessed by fluorescence, and the estimated necrosis volume based on CT with and without contrast.

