***Non-study Treatments***

Patients may receive all concomitant therapy deemed to provide adequate supportive care at the investigator's discretion. All such medications or other treatments taken by the patient during the study (including those initiated prior to the start of the study) will be recorded in the patient's clinical notes and on the study case

report forms. No immunotherapy, hormonal therapy (excluding contraceptives and replacement steroids), or experimental medications will be permitted for three days post-phototherapy. Any disease progression requiring other forms of specific anti-tumor therapy will be a cause for early discontinuation in the study.

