## 6.2.2. Protection Against Risk

### ***Adverse Events (Definitions)***

An Adverse Event (AE) is defined as any untoward medical occurrence in a patient or clinical investigation subject administered a pharmaceutical product regardless of the causal relationship with this treatment. Any adverse event or concurrent illness experienced by a patient during any portion of the study will be described in detail, fully evaluated and recorded on an adverse event form in the case report form by the investigator.

An *Unexpected Adverse Event* is defined as an adverse drug event the nature or incidence of which is not consistent with applicable product information.

A *Serious Adverse Event (SAE)* is defined as any untoward medical occurrence that at any drug dose results in:

- Death
- Inpatient hospitalization or prolongation of hospitalization
- A life-threatening event
- Severe or permanent disability
- Cancer (other than cancers diagnosed prior to enrolment in studies involving patients with cancer)
- Congenital anomaly

Note that as defined above, serious events, expected or not, are not necessarily causally associated with the study treatment. Those occurring during treatment and up to one month post-treatment will be reported promptly, and if assessed as a Suspected Unexpected Serious Adverse Reaction (SUSAR) within the timeframes (as specified in the Clinical Trials Regulations 2004) will be reported promptly to the appropriate authorities including the independent Data Monitoring and Ethics Committee (DMEC, see Section 5 below). The ultimate decision for the continuation of the trial lies with the DMEC.

All adverse effects will be assessed for the following:

- Severity (according to NCI toxicity criteria)
- Causality
- Expectedness (see below)
- Seriousness (see above)

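### The safety of chemotherapy soon after PDT is a stated objective, but its timing is given in two ways, no safety assessment is scheduled from day 14 to month 3, and no analysis is attached

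*Combined protocol and SAP*

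**What the plan says.** Section c.1.a lists as its tertiary objective: "Evaluate the safety of chemotherapy given two days after PDT". Section c.1.b, after describing the CT two days after PDT (treatment day 3), says of patients that "they will be able to commence conventional palliative chemotherapy after that if they so wish within a week of PDT". Section b (Innovation) also treats chemotherapy as a choice: "For patients choosing additional conventional chemotherapy".

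On follow-up, c.1.d states: "All patients will be followed up on day 14 then at three, six and 12 months". Table 2 places symptom and adverse-event checks, examination and blood tests on days 2 and 3, on day 14, and at months 3, 6 and 12.

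On recording, the adverse event definitions in 6.2.2 state: "Any adverse event or concurrent illness experienced by a patient during any portion of the study will be described in detail". Of serious events they say: "Those occurring during treatment and up to one month post-treatment will be reported promptly". The section on non-study treatments requires that other therapy be written in the notes and case report forms, covering "All such medications or other treatments taken by the patient during the study". The secondary response evaluation in c.1.h adds a blood test for some patients: "CEA and/or CA19.9 4-weekly if elevated prior to therapy".

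The documents give no chemotherapy-safety endpoint, no chemotherapy-treated analysis set, no expected number of patients taking chemotherapy, and no analysis for this objective.

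**The concern.** Earlier chemotherapy is presented as one of the study's innovations: c.1.b contrasts it with a one-month bar in previous studies. The project summary says the trial will establish that giving chemotherapy almost immediately after PDT is safe, and the Specific Aims say the results will shape later combination trials. A reader will therefore expect the trial to yield usable toxicity data on the sequence.

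Three features weaken that. The interval in the objective is not the interval in the design. The exposed group is whoever chooses chemotherapy, so its size is unknown and its members may differ from the rest. And after day 14 the plan schedules no symptom check or blood count until month 3, so non-serious and laboratory toxicity in between enters the study data only if someone happens to report it or sends a result. A statement at the end that early chemotherapy was safe could rest on a small, mixed group with about one to one and a half weeks of scheduled observation on chemotherapy before month 3.

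**Working it through.** **The plan's own safety figure.** The only safety probability in the documents is in the early-termination criteria: at least 13 of 25 patients with grade 3/4 toxicity, stated probability 0.02 if the true rate is 30%. The exact binomial tail is P(X ≥ 13 | n = 25, p = 0.30) = 0.0175, which rounds to 0.02, so the figure is reproduced. The rule counts all patients. It says nothing specific about those who take chemotherapy.

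**Timing.** PDT is day 1 (Table 2). The CT is on day 3, two days after PDT. A week after PDT is day 8. The permitted start therefore runs from about day 3 to about day 8, and the objective's two days is its first day.

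**Scheduled assessment after a first dose.**
- First dose to the day-14 visit: 14 − 3 = 11 days at the longest, 14 − 8 = 6 days at the shortest.
- Day 14 to month 3: 90 − 14 = 76 days, or 91 − 14 = 77 days if month 3 is taken as day 91.
- Prompt reporting of serious events, if one month is taken as 30 days from PDT (an assumption; the start of the month is not defined): 30 − 2 = 28 days after the earliest first dose, 30 − 7 = 23 days after the latest.

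**What fills the 76 to 77 days.**

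| Provision | What it gives | What it does not give |
|---|---|---|
| Adverse-event recording throughout (6.2.2) | Any event that comes to the investigator's notice | A scheduled contact |
| Prompt reporting of serious events to one month | Serious events to about 23 to 28 days after first dose | Non-serious toxicity, dose delays |
| Non-study treatments on the case report form | Exposure to chemotherapy | Its toxicity |
| 4-weekly CEA and/or CA19.9 | A blood draw if the marker was raised before therapy | A blood count or symptom review, as written |
| Quarterly committee review (6.5) | Review of collected data | New collection |

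**Precision.** The number taking chemotherapy is not stated, so a range is assumed from the planned 30. With no events of a given type, the one-sided 95% upper limit is 1 − 0.05^(1/n). The chance of seeing at least one event when the true rate is 10% is 1 − 0.9^n.

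| Patients on chemotherapy (assumed) | Upper limit with 0 events | Chance of ≥ 1 event at a 10% rate |
|---|---|---|
| 30 | 9.5% | 96% |
| 15 | 18.1% | 79% |
| 10 | 25.9% | 65% |

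Patients who start exactly two days after PDT would be fewer still if starts spread over the window.

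**The case against.** The best reply is that the objective's two days is shorthand. It is the earliest permitted point, section b describes the aim as giving chemotherapy much sooner after PDT than before, and chemotherapy is openly a matter of choice. This is fair: the mismatch is loose wording rather than a conflict that breaks the design. It still leaves the exposure undefined for analysis.

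The second reply is that observation is not missing. A reader might infer from Table 2 that the combination is hardly observed, or that safety data collection ends at one month. The documents do not support either. Events are recorded over the whole study, the adverse event form is completed for every treatment-emergent event, investigators must comment on out-of-range laboratory values, patients who cannot return are telephoned about adverse events and hospitalization, and safety is reviewed quarterly. The one-month limit concerns prompt reporting of serious events only. What stands is narrower: none of this schedules a contact or a blood count between day 14 and month 3.

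Three other stronger readings also go too far. Chemotherapy may not start at any time in the first week, because the start follows the day-3 CT. That the earliest starters are the fittest is plausible but inferred. And no cycle length is given, so it cannot be said how many cycles fall in the gap.

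Finally, the objective is tertiary and unpowered, and no decision rule depends on it. That lowers the priority. It does not answer the point.

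**Conclusion.** The point holds in limited form. The objective and the design section give different timings and must be reconciled; this review takes no view on which is right. After a first dose there is one scheduled safety assessment, 6 to 11 days later, and then none for about 76 to 77 days. In that interval non-serious and laboratory toxicity is collected only passively, in a subset of unstated size that may be self-selected, and no analysis is specified.

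The day counts rest on PDT as day 1 and month 3 as day 90 or 91. The upper limits of 9.5% to 25.9% rest on assumed uptake. They show how cautiously a clean result should be worded. They do not measure what the fix would gain, since the fix does not add patients. The weakness is in scheduled collection and in the missing analysis, not an absence of safety monitoring. It is a cheap improvement of lower priority.

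**What to change.** 1. Reconcile c.1.a and c.1.b on when chemotherapy is given relative to PDT. The investigators decide the timing.
2. State that chemotherapy safety will be reported descriptively, by actual days from PDT to first dose, with the number exposed and exact confidence limits. Record the reason for a later start or no start. Make no causal comparison between patients who start and those who do not, because the choice may depend on how they fared after PDT.
3. Add one adverse-event telephone contact at about day 30. Section c.1.d already uses the telephone for patients who cannot attend.
4. Copy blood counts, dose delays and admissions from routine chemotherapy records into the case report form up to month 3.

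The cost is protocol wording, one call per patient and some extra data entry, including obtaining records where chemotherapy is given elsewhere. No new visit or procedure is needed.
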